14.1.2. Recording Adverse Events

It is the responsibility of the Investigator to document all AEs (i.e., PTAEs and TEAEs) with an onset after the subject signs the ICF. For the purpose of this study, all AEs that occur through Day 30 after surgery must be recorded regardless of whether or not they are considered related to

study drug. Whenever feasible, AE terms should be documented as medical diagnoses (highest possible level of integration); otherwise, the AEs should be reported separately as individual signs or symptoms. Only one AE per line should be recorded in the AE CRF; for example, an AE of nausea and vomiting should be listed as two separate events: the event of nausea and the event of vomiting. If a diagnosis is established after symptoms are recorded on the AE CRF, the diagnosis should be recorded and the symptoms collapsed (removed; i.e., lined through and initialed). Whenever possible, abnormal laboratory results should be reported as their clinical corollary (e.g., low potassium should be recorded as hypokalemia).

All AEs will be followed through progression of their severity. For example, if an AE is reported as mild in severity but changes to moderate, the AE of mild will have an end date when the severity changes to moderate. A new AE record with a moderate severity will be created with a start date that is the same as the end date of the mild AE.

Any condition noted before the subject signs the ICF will be listed as Medical History and is considered a pre-existing condition. If a pre-existing condition changes (i.e., becomes more severe or more frequent) at any time after the subject signs the ICF it is considered an AE. Note: A change in treatment for a pre-existing condition (e.g., new high blood pressure medication), does not necessarily indicate an AE.

Information recorded on the AE CRF will include the AE term, the date and time of onset, severity, seriousness, relationship to study drug, action taken with subject due to AE, and the outcome of the AE, including the date and time of resolution, if applicable.

14.1.3. Severity of Adverse Events

In general, the severity of an AE should be categorized using the following guidelines:

Mild: An AE that is easily tolerated by the subject, causing minimal discomfort and not interfering with everyday activities.

Moderate: An AE that is discomforting and interferes with normal everyday activities.

Severe: An AE that prevents normal everyday activities.

14.1.4. Relationship of Adverse Events to Study Drug

The Investigator will assess the relationship of the AE to study drug after careful medical consideration on a case-by-case basis. General guidelines are provided below.

Unlikely: A clinical event with a temporal relationship to study drug administration which makes a causal relationship improbable and in which other drugs, chemicals, or underlying disease provide a plausible explanation;

Possible: A clinical event with a reasonable time sequence to administration of the study drug but which could also be explained by a concurrent disease or other drugs or chemicals;

Probable: A clinical event with a reasonable time sequence to administration of the study drug unlikely to be attributed to a concurrent disease or other drugs or chemicals and which follows a clinically reasonable response on withdrawal (dechallenge); or

Definite: The pharmacological properties of the study drug(s) or of the substance class, and the course of the AE after dechallenge and, if applicable, after rechallenge, and/or specific test indicate involvement of the study drug(s) in the occurrence/worsening of the AE, and no indication of other causes exists.

14.1.5. Outcome of Adverse Events

The Investigator will assess the outcome of the AE after careful medical consideration, on a case-by-case basis. General guidelines are provided below:

Recovered/Resolved: The event resolved and the subject recovered from the AE.

Recovered/Resolved with Sequelae: The initial event resolved, but has a continuing abnormal condition as a result of the AE.

Not Recovered/Not Resolved: At the time of last assessment, the event was ongoing, with an undetermined outcome. Note: ongoing AEs are not to be considered resolved as a result of death.

Recovering/Resolving: At the time of last assessment, the event was decreasing in frequency, severity, etc., and a resolution was expected.

Fatal: The AE directly caused death.

Unknown: There was an inability to access the subject or the subject's records to determine the outcome (e.g., subject withdrew consent or was lost to follow-up).

14.1.6. Action Taken with Subject due to an Adverse Event

The Investigator will provide any actions taken regarding the subject (e.g., treatment, diagnostic tests, laboratory tests, or therapy) for each reported AE.

- None.
- Medication.
- Non-pharmaceutical therapy. (The specific therapy used must be recorded in the CRF.)
- Discontinued from study.
- Other. (The specific action taken must be recorded.)

14.2. Serious Adverse Events

14.2.1. Definition of a Serious Adverse Event

Definition of a Serious Adverse Event (SAE): An AE is considered “serious” if, in the view of either the Investigator or Sponsor, it results in any of the following outcomes:

- Death¹.
- A life-threatening adverse event².
- Inpatient hospitalization or prolongation of existing hospitalization³.
- A persistent or significant incapacity⁴.
- Congenital anomaly/birth defect.
- Medically significant⁵.

¹Death: Any event resulting in a subject’s death must be reported as an SAE. However, death, in and of itself, is not an AE; it is an outcome. The cause of death is the AE. Therefore, the Investigator should make every effort to obtain and document the cause of death for all subjects who die during the study. If, despite all efforts, the cause of death remains unknown, the AE should be documented as an “unspecified fatal event.”

²Life-threatening: An AE is considered life-threatening if, in the view of either the Investigator or Sponsor, its occurrence places the subject at immediate risk of death. It does not include an AE that had it occurred in a more severe form might have caused death.

³Hospitalization: It should be noted that hospitalization, in and of itself, does not represent an SAE. It is the AE leading to the subject’s hospitalization that becomes “serious” when it requires inpatient care. Consequently, an SAE should not be reported in case of preplanned hospitalizations for a pre-existing condition that did not worsen during the study. However, any medical condition that delays a subject’s discharge from the hospital (i.e., prolonged hospitalization) or requires the subject to be readmitted should be reported as an SAE.

⁴Persistent or significant incapacity: A substantial disruption of a person’s ability to conduct normal life functions.

⁵Medically Significant: Important medical events that may not result in death, be life-threatening, or require hospitalization, may be considered serious when, based upon appropriate medical judgment, they may jeopardize the subject and may require medical or surgical intervention to prevent one of the outcomes listed in this definition. Examples of such medically significant events include allergic bronchospasm requiring intensive treatment in an emergency room or at home, blood dyscrasias or convulsions that do not result in inpatient hospitalization, or the development of drug dependency or drug abuse.

14.2.2. Reporting Serious Adverse Events

Any SAE or death that occurs at any time after the subject signs the ICF through Day 30, whether or not related to EXPAREL, must be reported by the Investigator or designee to Pacira Drug Safety within 24 hours of discovery by either email ([contact]) or [contact]). In addition, the Investigator or designee is encouraged to contact the Medical Monitor to discuss the case, as needed, at [contact].

Investigators should not wait to receive additional information to fully document the event before notifying Pacira Drug Safety or designee of the SAE. The fax or email report should be followed by a full written summary using the SAE Form detailing relevant aspects of the SAE in question. Where applicable, information from relevant hospital records and autopsy reports should be obtained and all patient-identifying information redacted prior to forwarding to Pacira. In the event of a fatal or life-threatening SAE, any required follow-up must be provided to Pacira Drug Safety or designee immediately. The Investigator will follow all SAEs until resolved or the condition stabilizes and further follow-up is not warranted.

If the Investigator is made aware of any SAEs after Day 30, these should also be reported to Pacira Drug Safety or designee provided the SAE is considered related to EXPAREL. The site would then provide a completed SAE form within 1 business day and the event would be followed until resolution, or until adequate stabilization is met.

15. STATISTICAL METHODS

A comprehensive statistical analysis plan (SAP) will be developed for this study.

15.1. Study Hypothesis

The primary null hypothesis is:

H_0 : The means of the AUC of the NRS pain intensity scores through 48 hours are not different between the EXPAREL and placebo groups.

The alternative hypothesis is:

H_A : The mean AUC of the NRS pain intensity scores through 48 hours for the EXPAREL group is less than that of the placebo group.

15.2. Study Endpoints

The endpoints to be assessed in this study are listed in [Section 12.2](#) (Efficacy Endpoints), [Section 12.4](#) (PK Endpoints), and [Section 12.6](#) (Safety Endpoints).

15.3. Determination of Sample Size

In previous wound infiltrations studies in hemorrhoidectomy and bunionectomy, the difference between treatment groups in mean AUC from 0 to 48 hours or NRS pain intensity scores varied from 20 to 103. The standard deviations varied from 100 to 128. A sample size of 50 in each group will have 90% power to detect a difference in means of 66 assuming that the common standard deviation is 100 using a two group t-test with a 0.05 two-sided significance level. A sample size of 50 in each group will have 90% power to detect a difference in means of 86 assuming that the common standard deviation is 130 using a two group t-test with a 0.05 two-sided significance level.

However, the EXPAREL group will randomize approximately 100 subjects to lower the AE detection threshold for the safety database to 3%. The sample size for placebo was increased due to the additional collection of NRS pain intensity score immediately prior to all requests for rescue medication through 96 hours. The placebo sample size was increased to ensure that there are at least 50 subjects treated in both the EXPAREL and placebo under the current protocol amendment. It is expected that the sample size will be approximately 175 subjects resulting in a 2:1 ratio of EXPAREL to placebo subjects.

15.4. Analysis Populations

The following analysis sets are planned:

Safety: The safety analysis set will include all subjects who receive study drug and will be based on actual treatment received.

Efficacy: The efficacy analysis set will include all subjects in the safety analysis set who undergo the planned surgery and will be based on randomized treatment, regardless of actual treatment received.

Pharmacokinetic: The PK analysis set will include all subjects in the safety analysis set who receive EXPAREL, provide sufficient samples to allow for calculation of PK parameters required for analysis, and do not have significant protocol deviations that may invalidate or bias the results.

15.5. Handling Subject Dropouts and Discontinuations

For the calculation of the AUC of NRS pain intensity scores through any of the time periods, the following methods will be used for imputing missing data:

Missing scores before the first non-missing score will be replaced by the median score at the missing timepoint from other subjects in the same treatment group. Missing scores after the last non-missing score will be replaced by the last non-missing score (last observation carried forward). Missing scores between two non-missing scores will use linear interpolation to replace the missing score.

Additional methods for dealing with missing data will be described in the SAP.

15.6. Statistical Analyses

15.6.1. Baseline Characteristics

Demographic and baseline characteristics will be summarized by treatment group.

15.6.2. Study Compliance

The percentage of subjects in each analysis set and the percentage who fail to complete the study (as well as the reasons for discontinuation) will be displayed by treatment group.

15.6.3. Efficacy Analyses

All efficacy analyses will be based on randomized treatment, regardless of actual treatment received.

15.6.3.1 Primary Efficacy Measures

The primary efficacy measure in this study is the AUC of the NRS pain intensity scores through 48 hours.

For the AUC of the NRS pain intensity scores through 48 hours, EXPAREL will be compared to placebo using analysis of variance (ANOVA) with treatment as the main effect. Based on the model, the difference between the treatment groups will be estimated along with the 2-sided 95% confidence intervals (CI).

Handling of Subjects Requiring Rescue Medication

For the AUC of the NRS pain intensity scores, prior to analysis the windowed Worst-Observation-Carried-Forward (wWOCF) imputation method will be applied. For subjects who take opioid rescue pain medication, their NRS pain intensity scores recorded within the window of controlled type of rescue medication (6 hours for PO oxycodone) will be replaced by the ‘worst’ observation. The worst observation will be the highest score in the time interval from the end of surgery up to the time prior to taking their first rescue pain medication. Note that NRS

pain intensity scores in the window that are higher than the worst value prior to opioid rescue pain medication will not be overwritten. If no NRS pain intensity score is available prior to the first opioid rescue pain medication, the worst observation from all available measurements within the same treatment arm will be used instead.

15.6.3.2 Secondary Efficacy Measures

The secondary efficacy measures will be analyzed using a hierarchical fixed-sequence stepwise testing procedure. To protect the Type 1 error rate, the testing will be performed in a sequentially rejective fashion. If the first test is significant at the 0.05 level, then, and only then, the next secondary efficacy measure will be tested, and so forth. The results will be declared statistically significant at the 0.05 significance level.

Continuous Measures of Efficacy

For the AUC of pain intensity scores, missing data will be imputed as described in [Section 15.5](#) and fully described in the SAP.

For the integrated rank assessment that uses total amount of postsurgical opioids consumed through 48 hours, opioid medications will be converted to an IV morphine equivalent amount. All opioids consumed through 48 hours will be included in the analysis.

Summary statistics for each measure will be shown at each timepoint by treatment group. To test for significant differences between EXPAREL and placebo with respect to continuous measures of efficacy, an ANOVA with treatment as the main effect will be used. Based on the model, EXPAREL will be compared to placebo and two-sided CIs about the difference will be presented.

Categorical Measures of Efficacy

For categorizing subjects as pain-free, the NRS pain intensity score must be 0 or 1 at the assessed timepoint.

The proportion of subjects in each category will be calculated and summarized at each timepoint by treatment group. A chi-square test or Wilcoxon Rank Sum test will be used to compare EXPAREL to placebo.

Time to Event Measures of Efficacy

The time from start of study drug administration to the first use of an opioid rescue medication through 96 hours will be summarized with Kaplan-Meier estimates. A log-rank test will be used to compare EXPAREL to placebo.

15.6.4. Pharmacokinetic Analyses

Pharmacokinetic parameters will be estimated from the PK analysis set, using plasma drug concentration-time profiles, where appropriate, by non-compartmental analysis.

Actual sampling time will be used for all calculations of the PK parameters. If there is any doubt in the actual time a sample was taken, then the scheduled time will be used.

Descriptive statistics will be used to summarize the PK parameters.

15.6.5. Safety Analyses

All safety analyses will be based on actual treatment received.

15.6.5.1 Adverse Events

Adverse event verbatim terms will be mapped to preferred terms and related system organ class using the Medical Dictionary for Regulatory Activities (MedDRA). Events that start prior to the start of study drug administration will be identified in listings only. Incidence rates of TEAEs and the proportion of subject prematurely withdrawn from the study due to a TEAE will be shown for each treatment group. Incidence rates will also be displayed for each treatment group for study drug-related TEAEs and by severity. Incidence rates of SAEs will also be shown for each treatment group. All incidence rates will be categorized and displayed by system organ class and preferred term.

15.6.5.2 Neurological Assessments

The proportion of subjects who are oriented at each timepoint will be summarized for each treatment group. The proportion of subjects who have at least one of the neurological events will be summarized for each treatment group.

15.6.5.3 Electrocardiograms

Descriptive statistics for each ECG parameter for baseline, each timepoint, and change from baseline at each timepoint will be summarized for each treatment group.

15.6.5.4 Vital Signs

Descriptive statistics for each vital sign for baseline, each timepoint, and change from baseline at each timepoint will be summarized for each treatment group.

15.7. Significance Testing

All tests will be two-sided and based on a significance level of 0.05.

18. APPENDICES

Appendix 1: Subject's Reported Pain (Numeric Rating Scale)

Subjects will be evaluated for pain using the NRS at 15 minutes, 30 minutes, 1, 2, 4, 6, 8, 12, 24, 48, 72, and 96 hours after the beginning of study drug administration, and immediately prior to each administration of rescue pain medication through 96 hours.

Pain Intensity Scale

On a scale of 0 to 10, where 0 = no pain and 10 = worst possible pain, how much pain are you having right now? (Circle one number only.)

Appendix 2: Subject Satisfaction with Postsurgical Pain Control (Likert Scale)

The subject's satisfaction with postsurgical pain control will be conducted at 24, 48, 72, and 96 hours after the beginning of study drug administration, and on Day 10.

Please circle the number below that best describes your overall satisfaction with the pain medication you received after surgery. (Circle one number only.)

1. Extremely dissatisfied
2. Dissatisfied
3. Neither satisfied nor dissatisfied
4. Satisfied
5. Extremely satisfied

Appendix 3: Postoperative Symptom Severity (PoSSe) Scale Questionnaire

Subjects will complete the PoSSe scale at 72 hours after the beginning of study drug administration and on Day 7.

PoSSe Scale

1. EATING

a. In the **last week**, has your operation affected your **enjoyment** of food?
(Please mark one box)
No, not at all Yes, a little Yes, very much

b. In the **last week**, for how many days were you unable to **open your mouth** normally because of your operation?
(Please mark one box)
0 days 1-2 days 3-4 days 5-6 days 7 days

2. SPEECH

a. In the **last week**, for how many days was your **voice** affected because of your operation?
(Please mark one box)
0 days 1-2 days 3-4 days 5-6 days 7 days

b. On the **worst day of the last week**, how badly was your **speech** affected by your operation?
(Please mark one box)
Not at all Slightly Moderately Severely Unable to speak at all

3. SENSATION

a. Thinking of the **last week**, for how many days were your lips or tongue feeling **tingling** because of your operation?
(Please mark one box)
None at all 1-2 days 3-4 days 5-6 days 7 days

b. Thinking of the **last week**, for how many days were your lips or tongue feeling **numb** because of your operation?
(Please mark one box)
None at all 1-2 days 3-4 days 5-6 days 7 days

4. APPEARANCE

a. Thinking of the **last week**, for how many days were your face and/or neck **bruised** because of your operation?

(Please mark one box)

None at all 1-2 days 3-4 days 5-6 days 7 days

b. Thinking of the **last week**, for how many days were your face and/or neck **swollen** because of your operation?

(Please mark one box)

None at all 1-2 days 3-4 days 5-6 days 7 days

5. PAIN

a. Thinking of the **last week**, for how many days did you experience **pain** from your operation?

(Please mark one box)

None at all 1-2 days 3-4 days 5-6 days 7 days

b. Thinking of the **last week**, has the pain from your operation been controlled by **painkillers**?

(Please mark one box)

I have had no pain.

Yes, completely controlled.

Controlled mostly but still some discomfort.

Poorly controlled.

Not controlled at all.

6. SICKNESS

a. Thinking of the **last week**, for how many days did you **vomit** or **feel nauseated**?

(Please mark one box)

None at all 1-2 days 3-4 days 5-6 days 7 days

b. On the **worse day** of the last week, **how many times** did you vomit or feel nauseated?

(Please mark one box)

Not at all One day 2-3 times More than 3 times All the time (all day long)

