7.6.1.3. Tertiary Efficacy

- The AUC of the NRS pain intensity scores through 96 hours.
- Sum of pain intensity scores (SPIS) through 24, 48, 72, and 96 hours.
- The NRS pain intensity scores at each assessed timepoint and immediately prior to each request for rescue pain medication.
- The AUC of the NRS pain intensity scores from 24-48 and 48-72 hours.
- Percentage of pain-free subjects at each assessed timepoint using the NRS pain intensity score.
- Percentage of opioid-free subjects through 96 hours.
- Time to first opioid rescue medication.
- Integrated rank assessment using the NRS pain intensity score at 48 hours and the total amount of postsurgical opioids consumed through 48 hours (Silverman 1993)⁸.
- Overall assessment of the subject's satisfaction with postsurgical pain control (using a 5-point Likert scale) at 24, 48, 72, and 96 hours, and on Day 10.
- PoSSe scale mean total score at 72 hours and on Day 7.
- Number of unscheduled phone calls or office visits related to pain through Day 30.

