7.6.1.8. Postoperative Symptom Severity (PoSSe) Questionnaire

The PoSSe score is the total score of the weighted responses for each question. If a response is missing to any question in the PoSSe, the total score will not be calculated.

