| 4a: Days face or neck bruised | None at all 1-2 days 3-4 days 5-6 days 7 days | n (%) | XX (XX.X) XX (XX.X) XX (XX.X) XX (XX.X) XX (XX.X) | XX (XX.X) XX (XX.X) XX (XX.X) XX (XX.X) XX (XX.X) |
| 4b: Days face or neck swollen | None at all 1-2 days 3-4 days 5-6 days 7 days | n (%) | XX (XX.X) XX (XX.X) XX (XX.X) XX (XX.X) XX (XX.X) | XX (XX.X) XX (XX.X) XX (XX.X) XX (XX.X) XX (XX.X) |

Source: list SAS datasets used to create table
SAS X.Y

DDMONYYYYTHH:MM
program_name

Pacira Pharmaceuticals

(Page X of Y)

Protocol: 402-C-329

Table 14.2-12.2: Summary of Postoperative Symptom Severity (PoSSe) Questionnaire - Individual Question Score Tabulation - Primary Efficacy Analysis Set

Site: Overall

| Timepoint Question | Score | Statistic | EXPAREL [N=XX] | Placebo [N=XX] |
|---|--|-----------|---|---|
| 72 hour (continued) | | | | |
| 5 PAIN, in last week: | | | | |
| 5a: Days experience pain | 0 days 1-2 days 3-4 days 5-6 days 7 days | n (%) | XX (XX.X) XX (XX.X) XX (XX.X) XX (XX.X) XX (XX.X) | XX (XX.X) XX (XX.X) XX (XX.X) XX (XX.X) XX (XX.X) |
| 5b: Controlled by painkillers | Had no pain Completely controlled Some discomfort Poorly controlled No controlled | n (%) | XX (XX.X) XX (XX.X) XX (XX.X) XX (XX.X) XX (XX.X) | XX (XX.X) XX (XX.X) XX (XX.X) XX (XX.X) XX (XX.X) |
| 6 SICKNESS | | | | |
| 6a: Last week, days vomit/nauseated | 0 days 1-2 days 3-4 days 5-6 days 7 days | n (%) | XX (XX.X) XX (XX.X) XX (XX.X) XX (XX.X) XX (XX.X) | XX (XX.X) XX (XX.X) XX (XX.X) XX (XX.X) XX (XX.X) |
| 6b: Worst day, how many times vomit/nauseated | None One day 2-3 times > 3 times All the time | n (%) | XX (XX.X) XX (XX.X) XX (XX.X) XX (XX.X) XX (XX.X) | XX (XX.X) XX (XX.X) XX (XX.X) XX (XX.X) XX (XX.X) |

Source: list SAS datasets used to create table
SAS X.Y

DDMONYYYYTHH:MM
program_name

Pacira Pharmaceuticals

(Page X of Y)

Protocol: 402-C-329

Table 14.2-12.2: Summary of Postoperative Symptom Severity (PoSSe) Questionnaire - Individual Question Score Tabulation - Primary Efficacy Analysis Set

Site: Overall

| Timepoint Question | Score | Statistic | EXPAREL [N=XX] | Placebo [N=XX] |
|---|---|-----------|-------------------|-------------------|
| 72 hour (continued) | | | | |
| 7 INTERFERENCE DAILY ACTIVITIES, in last week | | | | |
| 7a: Prevent work/housework | Not at all Work suffered 1 day 2-6 days 7 days | n (%) | XX (XX.X) | XX (XX.X) |
| | | n (%) | XX (XX.X) | XX (XX.X) |
| | | n (%) | XX (XX.X) | XX (XX.X) |
| | | n (%) | XX (XX.X) | XX (XX.X) |

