SAS X.Y

DDMONYYYYTHH:MM

program_name

Pacira Pharmaceuticals
Listing 16.2-11.2: Postoperative Symptom Severity (PoSSe) Scale Questionnaire - Questions

(Page 1 of 2)

Protocol: 402-C-329

Eating:

- 1a. In the last week, has your operation affected your enjoyment of food?
[0]No, not at all; [5.25] Yes, a little; [10.5] Yes, very much
- 1b. In the last week, for how many days were you unable to open your mouth normally because of your operation?
[0]0 days; [2.63]1-2 days; [5.25]3-4 days; [7.88]5-6 days; [10.5] 7 days

Speech:

- 2a. In the last week, for how many days was your voice affected because of your operation?
[0]0 days; [1.25]1-2 days; [2.5]3-4 days; [3.75]5-6 days; [5] 7 days
- 2b. On the worst day of the last week, how badly was your speech affected by your operation?
[0]Not at all; [1.25]Slightly; [2.5]Moderately; [3.75]Severely; [5]Unable to speak at all

Sensation:

- 3a. Thinking of the last week, for how many days were your lips or tongue felling tingling because of your operation?
[0]None at all; [2]1-2 days; [4]3-4 days; [6]5-6 days; [8] 7 days
- 3b. Thinking of the last week, for how many days were you lips or tongue felling numb because of your operation?
[0]None at all; [2]1-2 days; [4]3-4 days; [6]5-6 days; [8] 7 days

Appearance:

- 4a. Thinking of the last wekk, for how many days were your face and/or neck bruised because of your operation?
[0]None at all; [1.5]1-2 days; [3]3-4 days; [4.5]5-6 days; [6] 7 days
- 4b. Thinking of the last week, for how many days were your face and/or neck swollen because of you operation?
[0]None at all; [1.5]1-2 days; [3]3-4 days; [4.5]5-6 days; [6] 7 days

Source: list SAS datasets used to create listing
SAS X.Y

DDMONYYYYTHH:MM
program_name

Pacira Pharmaceuticals (Page 2 of 2) Protocol: 402-C-329
Listing 16.2-11.2: Postoperative Symptom Severity (PoSSe) Scale Questionnaire - Questions

Pain:

5a. Thinking of the last week, for how many days did you experience pain from your operation?
[0]None at all; [2.38]1-2 days; [4.75]3-4 days; [7.13]5-6 days; [9.5] 7 days

5b. Thinking of the last week, has the pain from your operation been controlled by pain killers?
[0] I have had no pain; [2.38] Yes, completely controlled;
[4.75] Controlled mostly but still some discomfort; [7.13] Poorly controlled;
[9.5] Not controlled at all

Sickness:

6a. Thinking of the last week, for how many days did you vomit or feel nauseated?
[0]None at all; [1.25]1-2 days; [2.5]3-4 days; [3.75]5-6 days; [5] 7 days

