6b. On the worse day of the last week, how many times did you vomit or feel nauseated?
[0]None at all; [1.25]One day; [2.5]2-3 times; [3.75]More than 3 times;
[5]All the time (all day long)

Interference with daily activities:

7a. In the last week, did the operation prevent you from carrying out work/housework and other daily activities?
[0]None at all; [0.83]I could continue with my work, but my work suffered; [1.65]Yes, for 1 day;
[2.48]Yes, for 2-6 days; [3.3]Yes, for 7 days

7b. In the last week, have your leisure activities been affected by your operation? (including sports, hobbies and social life)
[0]Not affected by the operation; [0.83]Mildly affected by the operation;
[1.65]Moderately affected by the operation; [2.48]Severely affected by the operation;
[3.3]The operation prevented any social life at all

7c. Thinking of the last week, how badly did the pain affect your life?
[0]Not at all; [1.1]Slightly; [2.2]Moderately; [3.3]Severely

Source: list SAS datasets used to create listing
SAS X.Y

DDMONYYYYTHH:MM
program_name

Pacira Pharmaceuticals
(Page X of Y)
Listing 16.2-12: Day 30 Phone Contact - Pain-Related Calls/Visits - Randomized Subjects
Treatment: TTTTTTT

Protocol: 402-C-329

| Site | Subject | Date | Visit | Number of pain-related | | |
|------|----------|-----------|--------|------------------------|---------------|-------|
| | | | | Phone calls | Office Visits | Total |
| XXX | XXX-YYYY | DDMONYYYY | Day 7 | XX | XX | |
| | XXX-YYYY | DDMONYYYY | Day 10 | XX | XX | |
| | XXX-YYYY | DDMONYYYY | Day 30 | XX | XX | XXX |

Source: list SAS datasets used to create listing
SAS X.Y

DDMONYYYYTHH:MM
program_name

Pacira Pharmaceuticals
Listing 16.2-13: Neurological Assessment - Randomized Subjects
Treatment: TTTTTTT

Protocol: 402-C-329

| Site | Subject | Assessment | Date and Time Of Assessment | | | Time From Dose | | | Questions | | | | | |
|------|----------|-----------------|-----------------------------------|----------------|---------------------|----------------|-----|-----|-----------|-----|-----|--|--|--|
| | | | Scheduled (hr) | Actual (hr) | Deviation (mins) | 1 | 2 | 3 | 4 | 5 | 6 | | | |
| XXX | XXX-YYYY | DDMONYYYYTHH:MM | 0 | XX | X | XX | XXX | XXX | XXX | XXX | XXX | | | |
| | | DDMONYYYYTHH:MM | 0.25 | 0.XX | X | XX | XXX | XXX | XXX | XXX | XXX | | | |
| | | DDMONYYYYTHH:MM | 0.50 | 0.XX | X | XX | XXX | XXX | XXX | XXX | XXX | | | |
| | | DDMONYYYYTHH:MM | 1 | X | X | XX | XXX | XXX | XXX | XXX | XXX | | | |

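### PoSSe item 6b asks for a count of sickness episodes on the worst day, but its second option, scored 1.25, reads as a number of days: some subjects may be under-scored or leave the item blank, in a tertiary endpoint that is not tested

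*Protocol*

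**What the plan says.** The item appears in three places.

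- **Protocol, Appendix 3, item 6 (Sickness), part b.** The subject-facing form offers "Not at all One day 2-3 times More than 3 times All the time (all day long").
- **SAP Section 11.1, Table 14.2-12.2.** The shell has the rows "None One day 2-3 times > 3 times All the time".
- **SAP Section 11.2, Listing 16.2-11.2.** The stem is "6b. On the worse day of the last week, how many times did you vomit or feel nauseated", and the scores are "0]None at all; [1.25]One day; [2.5]2-3 times; [3.75]More than 3 times", with the top category given as "5]All the time (all day long").

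The item above it already asks for days: "6a. Thinking of the last week, for how many days did you vomit or feel nauseated".

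On use of the score, SAP Section 7.6.1.3 lists as a tertiary endpoint "PoSSe scale mean total score at 72 hours and on Day 7". SAP Section 7.6.1.8 adds: "If a response is missing to any question in the PoSSe, the total score will not be calculated". SAP Section 7.6.2.3 provides for description only of tertiary endpoints, and Section 7.6.2.3.10 also summarises the individual items.

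**The concern.** Four of the five answers to 6b describe frequency within one day; the second describes a duration. That allows two kinds of failure.

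First, a subject whose sickness was confined to a single day, but who was sick more than once on it, may take *One day* as the description that fits and receive the second-lowest score. Second, a subject with exactly one episode finds no option that plainly says so and may skip the item, which under Section 7.6.1.8 removes that subject's whole total.

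At stake are the PoSSe total at 72 hours and Day 7 and the 6b rows of the item table. A *One day* row there cannot be read with confidence as a count of one. Protocol Section 7.2 names nausea and vomiting among the opioid effects it is desirable to reduce, so the item bears on the product's rationale even though it carries little weight.

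**Working it through.** **1. What the second option was meant to be.** The 6b scores in Listing 16.2-11.2 are 0, 1.25, 2.5, 3.75 and 5. Equal steps on a five-category item with maximum 5 give 5 × k/4 for k = 0 to 4, that is 0, 1.25, 2.5, 3.75 and 5. The listed scores are reproduced exactly. The second option is therefore the step between none and 2-3 times, which in a list of counts is once.

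**2. Is it an extraction fault?** No. The same words stand in the protocol form, the SAP table shell and the SAP scoring listing.

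**3. Score error for one subject who ticks *One day*.** Error = 1.25 − score for the true frequency.

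| True frequency on the worst day | Intended score | Scored | Error | Share of item maximum (5) |
|---|---|---|---|---|
| Once | 1.25 | 1.25 | 0 | 0% |
| 2-3 times | 2.5 | 1.25 | −1.25 | 25% |
| More than 3 times | 3.75 | 1.25 | −2.5 | 50% |
| All day | 5 | 1.25 | −3.75 | 75% |

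**4. Against the total.** The item maxima in Listing 16.2-11.2 sum to 2×10.5 + 2×5 + 2×8 + 2×6 + 2×9.5 + 2×5 + 3×3.3 = 97.9. The errors are then 1.25/97.9 = 1.3%, 2.5/97.9 = 2.6% and 3.75/97.9 = 3.8% of the largest attainable total. (Listing 16.2-11.1 describes the total as running to 100%; that small discrepancy is a separate matter.)

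**5. Effect on an arm mean.** The documents give no misreading rate. Assume a share f of an arm ticks *One day* wrongly, with f from 5% to 30%. The fall in the arm's mean total is f × error:

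- true frequency 2-3 times: 0.05 × 1.25 = 0.06 to 0.30 × 1.25 = 0.38 points;
- more than 3 times: 0.05 × 2.5 = 0.13 to 0.30 × 2.5 = 0.75 points;
- all day: 0.05 × 3.75 = 0.19 to 0.30 × 3.75 = 1.13 points.

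Each line assumes that every misreader in the arm has the same true frequency. Only a difference in these shifts between arms would move the treatment comparison.

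**6. Blank answers.** Item 6b is one of 15 items and carries 5 of the 97.9 points, yet a blank there removes the total at that visit.

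**The case against.** The strongest reply is that context largely repairs the wording. The stem fixes a single day and asks for a number of times, and the odd option sits between none and 2-3 times. A subject with one episode will probably tick the box in between and get 1.25, the intended score. This stands. A reader might infer that a single episode must be mis-scored, as 0 or 2.5; the table above shows no error for a subject who ticks *One day*. What remains for that subject is the risk of a blank.

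Likewise, the 3.75-point case needs someone who felt sick all day to pass over an option that says so. It is an upper bound and should not be taken as typical.

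It can also be said that the opioid-effect question does not rest on 6b. Nausea and vomiting are recorded as adverse events (Protocol Section 14.1.2 uses them as its example), and TEAEs are tabulated by arm (SAP Section 7.7.4). That stands too. So does the fact that Table 14.2-12.2 will show how many subjects ticked *One day*; it cannot show how many of them meant once.

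Finally, PoSSe is a published scale cited by the protocol, and the documents do not show whether the wording comes from the source or was introduced locally. This does not remove the ambiguity or its scoring consequence, but the source should be checked before the form is changed.

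**Conclusion.** The point holds as a response-option error in a scored instrument. Where *One day* is ticked for repeated sickness on a single day, the subject is under-scored by 1.25 to 2.5 points, and by 3.75 only in the unlikely all-day case. Where the item is left blank, the total is lost. A single-episode subject who ticks *One day* is scored correctly.

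The reach is small. PoSSe is tertiary and descriptive, so the primary and secondary analyses, the alpha and the sample size are untouched. The number of subjects affected is not in the documents, and the arm-mean shifts above rest wholly on the assumed 5% to 30%. A reader might infer a biased treatment comparison because opioid use, and so nausea, may differ by arm. The documents give no misreading rate by arm, and neither the direction nor the size of such a bias can be derived from them.

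That once was intended is an inference from the order and the equal-step scores. It is a strong one, but it is subject to the check against the source scale.

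**What to change.** 1. Check the wording of 6b against the cited source scale.
2. Then change the second option to *Once* in Protocol Appendix 3, the CRF, SAP Table 14.2-12.2 and SAP Listing 16.2-11.2 together. Keep the score of 1.25; no weight changes.
3. For forms completed on the present wording, footnote the *One day* row in Table 14.2-12.2 and add one supportive summary of the PoSSe total without 6b (maximum 97.9 − 5 = 92.9). If that total requires only the other 14 items, it also recovers subjects who left only 6b blank. It discards correct 6b answers as well, so it should sit beside the planned total and not replace it.

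The cost is one word in four places, a footnote and one extra descriptive summary. The downside is two form versions within one descriptive endpoint, which the footnote should state.
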